#### **5.6.2.13. Assessment of neurodevelopmental status**

The parent(s)/LAR(s) will be asked to complete a standardised developmental screening tool known as ASQ-3 when the subject is 9 months and 18 months old [ASQ-3, 2016]. The ASQ-3 has been used globally and translated into different languages. The tool has been demonstrated to reliably and accurately identify children with delays who should receive further in-depth assessment. The ASQ-3 includes a series of questions designed to assess five areas of development: communication, gross motor, fine motor, problem solving, and personal-social. The questions target behaviours that are appropriate for particular developmental status. These behaviours are easy for the parent(s)/LAR(s) to observe and they are asked to indicate whether or not the subject can perform the behaviour. The ASQ-3 will be completed by the *investigator or designee with* the parent(s)/LAR(s) *during the study visits or phone call* when the subject is 9 and 18 months of age, via a paper questionnaire \*. These time- points comply with the recommended developmental screening assessment guidelines from the American Academy of Pediatrics [Council on Children with Disabilities, 2006]. *The investigator or designee may discuss the results with the parents if deemed necessary. (Amended 12 December 2016)*

The ASQ-3 has narrow age intervals (*9 months and 0 days through 9 months and 30 days and 17 months and 0 days through 18 months of age and 30 days*), so age must be calculated to the month and day from the date the ASQ-3 will be completed. **(Amended 12 December 2016)**

If a baby was born three or more weeks prematurely, the number of weeks premature should be subtracted from the child's actual age [ASQ, 2014]. Refer to the SPM for more details and examples.

Any subject who scores below the cut-off i.e., a score more than 2 Standard Deviations (SDs) below the mean score for the U.S. reference group (i.e., black zone in the score chart) in any of the five domains of the ASQ-3 (i.e., communication, gross motor, fine motor, problem solving, and personal-social) will be referred to a developmental specialist for formal neurodevelopmental assessment (e.g., using the Bayley Scale for Infant Development, Version III [BSID-III]) [Bayley-III, 2006]. An overall neurodevelopmental assessment in the areas of cognitive, language, motor, social-emotional and adaptive behaviour will be rendered using BSID-III. A BSID-III score

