- For a given subject and the analysis of solicited AEs, four days post-vaccination (Day 0-Day 3), missing or non-evaluable measurements will not be replaced. Therefore, the analysis of the solicited AEs based on the TVC will include only vaccinated subjects and doses with documented safety data (i.e., symptom screen completed).
- For a given subject, missing neurodevelopmental status will not be replaced. Therefore, an analysis will exclude subjects with missing or non-evaluable measurements

- For analysis of unsolicited AEs, such as SAEs or AEs by primary Medical Dictionary for Regulatory Activities (MedDRA) term, and for the analysis of concomitant medications, all vaccinated subjects will be considered. Subjects, whose parent(s)/LAR(s) do not report the event or the concomitant medication, will be considered as subjects without the event or the concomitant medication, respectively.
- For summaries reporting both solicited and unsolicited AEs, all vaccinated subjects will be considered. Subjects, whose parent(s)/LAR(s) do not report the event or the concomitant medication, will be considered as subjects without the event or the concomitant medication, respectively.

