9.2. Statistical Method

If all subjects with ASQ-3 score in the black zone for at least one domain have BSID-III results, the clopper and Pearson CI will be used for the % of subjects with neurodevelopmental impairment.

If some subjects with ASQ-3 score in the black zone for at least one domain have no BSID-III results, the Greenwood formula [S.Sawyer,2003] for censored BSID-III data

will be used to estimate the % of subjects with neurodevelopmental impairment and associated CI.

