Template 29 Percentage of subjects with ASQ-3 score in the black zone for Month 9, 18 (Total enrolled cohort)

Time point	Characteristics	Categories	dTpa Group					Control Group					
			N	n	%	95% CI		N	n	%	95% CI		
						LL	UL				LL	UL	
Month 9	Any domain	Yes											
		No											
	Communication	Yes											
		No											
	Fine motor	Yes											
		No											
	Problem solving	Yes											
		No											
	Personal-Social	Yes											
		No											
Month 18	Any domain	No											
	Communication	Yes											
		No											
	Fine motor	Yes											
		No											
	Problem solving	Yes											
		No											
	Personal-Social	Yes											
	Personal-Social	Yes											
		No											
	Month 9 or 18	Any domain	No										
		Communication	Yes										
			No										
Fine motor		Yes											
		No											
Problem solving		Yes											
		No											
Personal-Social	Yes												

CONFIDENTIAL

201334 [DTPA (BOOSTRIX) -049 BST: 048]
 Statistical Analysis Plan Final

Time point	Characteristics	Categories	dTpa Group					Control Group				
			N	n	%	95% CI		N	n	%	95% CI	
						LL	UL				LL	UL
	Personal-Social	Yes										
	Personal-Social											

dTpa Group = Infants born to mothers belonging to the dTpa Group in study 116945 [DTPA (BOOSTRIX)-047] where mothers received dTpa during pregnancy. All subjects in this group will receive Infanrix hexa co-administered with Prevenar 13 according to the routine national immunisation schedule.

Control Group = Infants born to mothers belonging to the Control group in study 116945 [DTPA (BOOSTRIX)-047] where mothers received placebo during pregnancy. All subjects in this group will receive Infanrix hexa co-administered with Prevenar 13 according to the routine national immunisation schedule.

N = number of subjects enrolled

n = number of subjects in a given category

% = $n / \text{Number of subjects with available results} \times 100$

LL, UL for percentage = Exact 95% Lower and Upper confidence limits

Template 30 Percentage of subjects with confirmed developmental delay as determined by BSID-III at Month 9, 18 (Total enrolled cohort)

Time point	Characteristics	Categories	dTpa Group						Control Group					
			N	n	%	95% CI		N	n	%	95% CI			
						LL	UL				LL	UL		
Month 9	Any domain	Yes												
		No												
		Missing												
	Cognitive	Yes												
		No												
		Missing												
	Language	Yes												
		No												
		Missing												

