	Motor	Yes												
		No												
		Missing												
	Emotional	Yes												
		No												
		Missing												
Behaviour	Yes													
	No													
	Missing													
Month 18	Any domain	Yes												
		No												
		Missing												
	Cognitive	Yes												
		No												
		Missing												
	Language	Yes												
		No												
		Missing												
	Motor	Yes												
		No												
		Missing												
	Emotional	Yes												
		No												
		Missing												
Behaviour	Yes													
	No													
	Missing													
Month 9 or 18	Any domain	Yes												
		No												
		Missing												
	Cognitive	Yes												
		No												
		Missing												
	Language	Yes												
		No												
		Missing												
	Motor	Yes												
		No												
		Missing												

CONFIDENTIAL

201334 [DTPA (BOOSTRIX) -049 BST: 048]
Statistical Analysis Plan Final

Time point	Characteristics	Categories	dTpa Group					Control Group				
			N	n	%	95% CI		N	n	%	95% CI	
						LL	UL				LL	UL
	Emotional	Yes										
		No										
		Missing										
	Behaviour	Yes										
		No										
		Missing										

dTpa Group = Infants born to mothers belonging to the dTpa Group in study 116945 [DTPA (BOOSTRIX)-047] where mothers received dTpa during pregnancy. All subjects in this group will receive Infanrix hexa co-administered with Prevenar 13 according to the routine national immunisation schedule.

Control Group = Infants born to mothers belonging to the Control group in study 116945 [DTPA (BOOSTRIX)-047] where mothers received placebo during pregnancy. All subjects in this group will receive Infanrix hexa co-administered with Prevenar 13 according to the routine national immunisation schedule.

N = number of subjects enrolled

n = number of subjects in a given category

% = $n / \text{Number of subjects with available results} \times 100$

LL, UL for percentage = Exact 95% Lower and Upper confidence limits

Missing: number of subjects with ASQ-3 score in the black zone which are not referred for the BSID III

Template 31 Proportion of subjects with neurodevelopmental delay (Total enrolled cohort)

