Group	Timing	N	ASQ-3 score in the black zone for at least one domain		At least one of the indicators of neurodevelopmental delay using BSID III among the infants referred for BSID III evaluation		Estimated proportion of infants with at least one of the indicators of neurodevelopmental delay using BSID-III				
			n/N	%	n'/N'	%	n/N x n'/N'	%	LL	UL	
DTPa group	Month 9										
	Month 18										
	Month 9 or 18										
Control group	Month 9										
	Month 18										
	Month 9 or 18										

N = number of subjects enrolled

n/N = number of subjects with ASQ-3 below cut off / number of enrolled subjects

n'/N' = number of subjects with at least one indicator of neurodevelopmental delay using BSID III / number of subjects referred for BSID III evaluation

% = proportion of subjects with neurodevelopmental impairment at x time point

n/N x n'/N' = the multiplication of the two proportions

95% CI = exact 95% confidence interval (Clopper Pearson or Greenwood formula); LL = lower limit, UL = upper limit

Template 32 Evolution graph for the pertussis antibodies (Adapted ATP cohort)

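### Template 31 divides by all enrolled infants against the SAP's own missing-data rule, leaves 'referred' open to two readings, and names a Greenwood interval with no usable limit at zero cases

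*SAP*

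**What the plan says.** Template 31 reports the estimated proportion of infants with at least one indicator of delay as n/N × n'/N', by group, at Month 9, Month 18 and Month 9 or 18.

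- **First factor:** "number of subjects with ASQ-3 below cut off / number of enrolled subjects".
- **Second factor:** "number of subjects with at least one indicator of neurodevelopmental delay using BSID III / number of subjects referred for BSID III evaluation".
- **Interval:** "exact 95% confidence interval (Clopper Pearson or Greenwood formula").

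Other parts of the plan bear on these definitions:

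- **SAP 5.4.1, handling of missing data:** "missing neurodevelopmental status will not be replaced. Therefore, an analysis will exclude subjects with missing or non-evaluable measurements".
- **Templates 29 and 30:** both show N as enrolled, but the percentage is n divided by "Number of subjects with available results". The Template 30 footnote describes its missing category as "number of subjects with ASQ-3 score in the black zone which are not referred for the BSID III".
- **SAP 9.2:** Clopper-Pearson applies if every black-zone infant has a BSID-III result. If some "have no BSID-III results, the Greenwood formula" for censored data is used instead. The product is not written out there, and the cited reference names both the Greenwood and the exponential Greenwood interval in its title.
- **Protocol 5.6.2.13:** any infant below the cut-off in any domain "will be referred to a developmental specialist for formal neurodevelopmental assessment (e.g., using the Bayley Scale for Infant Development".

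**The concern.** There are three separate defects.

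1. **The first denominator contradicts the SAP's own rule.** Dividing by enrolled infants treats a missing ASQ-3 as a normal one. Month 9 is little affected, because the questionnaire is completed at Visit 1. Month 18 is exposed, because infants who finish Visit 3 before 18 months need a later phone contact and some infants withdraw after Visit 1. The combined row inherits the problem.
2. **Referred has two workable meanings.** Under the protocol every black-zone infant is referred, and BSID-III is only an example of the assessment, so a referred infant may have no BSID-III result. The Template 30 footnote instead equates a missing BSID-III with not being referred, which would make referred mean assessed.
3. **The interval is mislabelled and incomplete.** Greenwood is a large-sample variance formula, so it is not exact. The SAP does not say whether the plain or the exponential form applies, and neither gives a usable upper limit when no tested infant is impaired.

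Neurodevelopmental status is a stated secondary objective, and the protocol calls the effect of maternal vaccination on it unknown. Two programmers could report different percentages from the same data, and both denominator departures lower the figure. If missingness differs between groups, the comparison of dTpa with Control is distorted too.

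**Working it through.** Template 31 is an empty shell, so there is no planned estimate to reproduce. As a method check, Clopper-Pearson limits recover the illustrative intervals in Templates 17 and 18: for example, 264/335 gives 74.0 to 83.1% and 1/329 gives 0.0 to 1.7%.

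**Inputs.** The 340 per group is the planned maximum in the protocol. All other counts are assumptions: 306 with ASQ-3 (10% missing), n = 36 in the black zone, all 36 referred, 24 with a BSID-III result, n' = 5 impaired.

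**Point estimate**

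| N | N' | Estimate |
|---|---|---|
| 340 enrolled | 36 (referred = all black-zone) | 36/340 × 5/36 = 5/340 = 1.5% |
| 340 enrolled | 24 (referred = assessed) | 36/340 × 5/24 = 2.2% |
| 306 with ASQ-3 | 24 with BSID-III | 36/306 × 5/24 = 2.5% |

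In the first row n cancels. The product is simply n'/N, and the missing BSID-III results receive no adjustment. Relative to the third row, the understatement is 1 − 1.47/2.45 = 40% or 1 − 2.21/2.45 = 10%.

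The third row itself assumes that untested black-zone infants resemble tested ones. If none of the 12 untested were impaired the figure is 5/306 = 1.6%; if all were, 17/306 = 5.6%.

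**Range.** The enrolled denominator multiplies the estimate by the fraction with an ASQ-3: 1.00 to 0.80 for 0 to 20% missing. If N' is all black-zone infants, the fraction tested multiplies it again. With 60 to 80% tested, the combined factor runs from 0.80 × 0.60 = 0.48 to 1.00 × 0.80 = 0.80.

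**Interval.** Write V = (N−n)/(Nn) + (N'−n')/(N'n'). The plain form is p ± 1.96·p·√V. The exponential form applies the same variance on the log(−log p) scale. With N = 306, n = 36, N' = 24, n' = 1:

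- p = 36/306 × 1/24 = 0.49%
- V = 0.0245 + 0.9583 = 0.9828, so √V = 0.991
- plain: −0.5% to 1.4%
- exponential: 0.05% to 2.5%

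At n' = 0 the second term of V divides by zero. The plain interval is undefined, or collapses to 0 to 0 because p = 0. The exponential form needs log p, which does not exist.

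**How often this matters.** 200,000 simulated groups were run for each of nine assumed scenarios: 306 assessed; 8, 12 or 16% in the black zone; 5, 10 or 20% of those impaired; 70% of black-zone infants tested at random.

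- No impaired infant found: 0.1 to 42% of trials.
- Coverage among trials with n' of at least 1: about 89 to 100% plain, 95 to 97% exponential.
- Coverage if zero-case trials count as failures: about 58 to 92% plain, 55 to 96% exponential.

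**An interval that works at zero.** MOVER for a ratio, p2/(1/p1), uses the two Clopper-Pearson intervals, where p1 = n/N and p2 = n'/N'. With 36/306 (8.38 to 15.91%) and 0/24 (0 to 14.25%), 1/p1 = 8.5 with lower limit 1/0.1591 = 6.28. The upper limit is 0.1425/√[6.28 × (2 × 8.5 − 6.28)] = 0.1425/8.21 = 1.7%. In the nine scenarios it covered 97 to 99%, zero-case trials included.

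**The case against.** The strongest reply is that the body of the SAP already governs. Section 5.4.1 excludes infants with missing status, Templates 29 and 30 follow it, and the opening of Annex 3 says the mock displays are illustrative and may be adapted. But Template 31 is the only place in the documents where the product estimator is defined, and it spells out the enrolled denominator rather than leaving it implied. Changing an estimator's denominator is hardly an editorial adjustment.

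Second, the 40% figure needs the reading of referred that makes the censoring method in SAP 9.2 pointless, so a sensible programmer would take it to mean assessed. That is fair: on that reading the second factor is sound and the worked understatement is 10%. The larger figure belongs only to the other reading, which is nevertheless what the protocol's referral rule literally gives.

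Third, Templates 29 and 30 still give exact limits, and Clopper-Pearson applies when every black-zone infant is tested. This correctly confines the zero-case gap to the Greenwood branch. It does not close it, because neither template bounds the overall impairment proportion.

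Fourth, the bare words Greenwood formula may be read as the plain form. Perhaps, but the SAP does not write it out, and the plain form can give a negative lower limit, as shown above.

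Finally, MOVER is one choice among several. That stands, and it is offered as an example. The Greenwood coverage conditional on at least one case is also not directly comparable with the MOVER figures, which include all trials; for that reason both counts are shown for Greenwood.

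**Conclusion.** The concern holds and should be fixed. The enrolled denominator contradicts SAP 5.4.1 and the adjacent templates. It understates impairment by the fraction of infants without an ASQ-3: 10% in the worked case, 0 to 20% over the range considered. If referred means every black-zone infant, the loss rises to 40% in the worked case and to between 20% and 52% over the range. Calling Greenwood exact is wrong, and in the Greenwood branch the plan yields no usable upper limit at zero cases, an outcome seen in 0.1 to 42% of simulated trials. All rates are assumptions, since the documents give none. The direction of the denominator effects does not depend on them. The endpoint is secondary and every analysis is descriptive, so no error rate, sample size or primary conclusion changes.

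**What to change.** In Template 31 and SAP 9.2:

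- Write the product estimator into SAP 9.2, with N = infants with an available ASQ-3 at that time point. For Month 9 or 18, say whether one result or both are required.
- Set N' = black-zone infants with a BSID-III result, and align the Template 30 description of missing with it.
- State the assumption that untested black-zone infants resemble tested ones, and show the black-zone, referred and tested counts by group.
- Name one interval form that is defined at n' = 0, such as MOVER built from the two Clopper-Pearson intervals, and stop describing Greenwood as exact.

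The cost is SAP wording and programming, with no new data. The reported percentage may be less favourable, and the interval may be wider than plain Greenwood.
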